### C. Measurement / Instrumentation

To facilitate adherence to the 12-hour nicotine abstinence (verified via exhaled carbon monoxide [abstinence range = 3–4 ppm]), efforts will be made to complete all study visits in the morning hours (~7:00 AM–11:00 AM), near the participant's typical waking time. Randomization to condition order will be completed prior to study Visit 1. To ensure eligibility, pregnancy exclusion will be confirmed with a urine test (pregnancy tests will be completed at each visit throughout the study). Questionnaires will provide basic demographic and tobacco use history information. Participants will complete the pre-smoking respiratory assessments (spirometry and NELF collection). Spirometry will be completed in the standing position. Nasal Epithelial Lining Fluid (NELF) samples will be collected as described before. Briefly, the absorbent matrix cut to fit within the nasal passages will be inserted into the inferior nasal turbinate, and the matrix will be clamped in place with a padded nose clamp for 2 min after which the strips will be removed and placed into microfuge tubes and frozen. Samples will be extracted for assessment of inflammatory mediators (cytokines and chemokines; e.g., IL-6, IL-8), mediators of host defense status (IP-10, IL-1 $\beta$ , IFN $\gamma$ ) via multi-plex (Mesoscale Diagnostics). Then, participants will move to our negative pressure room to complete the first smoking session. Puffing Topography will be measured with a validated cigarette puff topography device (eTOP®) that records puff count, puff duration, inter-puff interval, puff flow rate, puff volume, and total puff volume. Participants will be instructed to smoke the study cigarette. Then, questionnaires (i.e., pre/post smoking) will capture specific behavioral and subjective effects associated with abuse liability, specifically as it relates to cooling perception (Table 1). Appeal and Sensory Quality will require participants to rate each product on visual analog scales (range, 0-100; liking and willingness to use again) and sensory characteristics (e.g., olfactory response, somatosensory responses, flavor intensity (very intense – no intensity), sensation intensity (very intense – no intensity), pleasantness of taste + sensation (very pleasant – very unpleasant, cooling power/intensity). The Drug Effects Questionnaire (DEQ) will be used to rate acute responses to the cigarette on visual analog scales (range, 0 “not at all” – 100 “extremely”). Items assess liking/wanting (the average of “I feel good cigarette effects,” “I want more of that cigarette I received,” “I feel the cigarette strength,” and “I like the cigarette effect”). Modified Cigarette Evaluation Questionnaire (mCEQ) will be used to measure domains of reinforcement (vaping satisfaction, psychological rewards, and aversion; e.g., “Was the product satisfying?” on a 7-point scale (e.g., 1 “not at all”, 4 “moderately”, 7 “extremely”). Nicotine withdrawal will be assessed using the empirically validated 15-item version of the Minnesota Nicotine Withdrawal Scale (MNWS). The Cigarette Purchase Task will assess economic demand (puffs) via questionnaire. During this questionnaire, participants will be asked to indicate the quantity of puffs they would hypothetically purchase and use if it was available at incrementally increasing prices ranging from \$0 (free) to \$100. Participants will be instructed to assume they were purchasing cigarette puffs for their consumption in 24 hours. Finally, participants will be presented with a second ad-lib smoking task (i.e., forced-choice task) where the participant will have the opportunity to choose between their usual brand cigarette and the study cigarette which will determine if the study product

is preferred over their usual brand cigarette.

Table 1. Study Measures and Outcome Variables			
	Study Session		
Measures	1	2	3
Sociodemographic measures	X		
Tobacco use history/nicotine dependence	X	X	X
Exhaled carbon monoxide	X	X	X
Respiratory Assessment (pre/post smoking)			
Spirometry	X	X	X
Nasal epithelial lining fluid (NELF)	X	X	X
Abuse Liability			
Smoking Topography	X	X	X
Appeal and Sensory Characteristics	X	X	X
Drug effects/liking	X	X	X
Modified Cigarette Evaluation Questionnaire (mCEQ)	X	X	X
Cigarette Purchase Task	X	X	X
Minnesota Nicotine Withdrawal Scale	X	X	X
Product Comparison			
Forced Choice Task	X	X	X

#### D. Detailed Study Procedures

Synthetic cooling agents (WS-3 and WS-23) added to cigarettes have the potential to increase the appeal and toxicity of combustible cigarettes as they are poised to serve as a flavorless menthol replacement. Importantly, these products benefit from an existing data gap, because evidence that may be needed to inform regulatory actions or product standards for the protection of public health is sorely lacking. This timely and innovative pilot study will address two key unknowns about synthetic cooling agents added to cigarettes. First, we will determine the amount and type of additives in these new cigarette products, while also examining non-menthol and menthol cigarettes. Next, using a double-blind randomized crossover trial, we will examine the impact of synthetic cooling agents on the appeal and abuse liability among young adult smokers (aged 21 – 29; N = 25). Participants will complete three clinic visits in which they will be randomized to smoke (first session) a same-brand cigarette in one of three variations: 1) non-menthol cigarette (control condition), 2) menthol cigarette, or 3) synthetic cooling agent cigarette. Questionnaires will assess appeal and sensory characteristics, and puffing topography will be collected during each session to examine differences in puffing behavior by cigarette type. To assess economic demand for the study product, participants will also complete a forced choice task for a secondary ad-lib smoking session where they can choose between the participant's usual brand cigarette and the study cigarette. Finally, as an exploratory aim, we will examine potential acute differences in pulmonary function (i.e., spirometry) and inflammation (i.e., nasal epithelial lining fluid [NELF]) before and after the first smoking session. Findings will constitute preliminary data to support a larger R01 application which will be aimed at informing FDA rulemaking surrounding the use of synthetic cooling agent additives in combustible cigarettes.

**Phone Screening:** All advertisements (see “Recruitment and Informed Consent” procedures below)

will have a phone number for RAs, QR code, and a direct link to the study screener. Trained RAs will provide a brief description of the study, screen the for eligibility while coding the answers into REDCap, and for eligible participants, schedule the first visit and provide directions to the study site. To provide some control over daily fluctuations in nicotine craving and withdrawal and to facilitate adherence to the 12-hour nicotine abstinence, efforts will be made to complete all study visits in the morning hours (~8:00–11:00 AM), near the participant's typical waking time.

**Study Randomization and Blinding Procedures:** Each participant will receive a randomized ordering developed using a random sequence generator. The Random sequence generator will be conducted by the study PI. Staff who will **not** interact with participants will prepare the study products in the randomized order sequence prior to each visit. Participants and data collection staff will be blinded to the order/conditions administered at each trial. The sequence list and subsequent participant ID numbers will be kept separate from data collection staff and will only be accessible in REDCap by staff who will not be interacting with participants.

**NELF Collection and Training:** Data collection staff will be trained by [name] to conduct the NELF collection procedures. A training video will also be provided as an ad-hoc reference for study staff. Pre-made NELF collection kits will be provided by The University of North Carolina at Chapel Hill from [name] (collaborator and colleague of [name]). To collect the sample, the nares are briefly moistened with 0.1 mL of 0.9% sterile, normal saline solution. Pre-cut Leukosorb strips are inserted into the nare at the inferior nasal turbinate along the anterior side until the indicator mark reaches the base of the nare. A padded nose clip will be applied to maintain the strip in the nose and to ensure maximum surface area of the strip with the nasal mucosa. The strip remains in the nare for 2 minutes. Strips containing NELF are then removed from the nostril, placed in microcentrifuge tubes, and frozen at -80 °C until analysis. These procedures have been utilized in [name] (PI) previous remote data collection studies by participants themselves via video conferencing software (e.g., zoom). Eight-five percent of participants in these past studies reported self-collection of this sampling procedures as "easy."

**Study Visit 1:** To ensure eligibility pregnancy exclusion will be confirmed with a urine test (pregnancy tests will be completed at each visit throughout the study). We will also ask participants to provide an exhaled breath sample to determine adherence to 12-hour nicotine abstinence (exhaled carbon monoxide [eCO]).

Informed consent will be obtained, and participants will provide basic demographic and product use history information. At the start of each visit, we will assess participants' height, weight, and blood pressure. Next, participants will complete computer-based spirometry testing and airwave oscillometry, which will measure central obstruction, peripheral obstruction, and dynamic collapse. Participants will also provide the first of two NELF samples. Then, participants will move to our negative pressure vaping room to complete the first smoking session and will be randomized to use the first product of the three conditions (i.e., non-menthol control; menthol; synthetic cooling agent). The study RA will connect the study to the topography device. Puff Topography will be measured with a validated puff topography device. The device uses a pressure transducer integrated into a plastic holder to produce measures of puff count, puff duration, inter-puff-interval, puff flow rate, average puff volume, and total puff volume. Participants will be instructed to smoke ad libitum. Next, participants will repeat the respiratory assessment, provide the final NELF sample, and complete questionnaires (see table 1) to capture specific domains (i.e., perceived effects, behavioral) associated with abuse liability. Lastly, participants will return to the negative pressure rooms to participant in the final smoking session. Participants will complete a forced choice task, in which they will choose if they would prefer to smoke their usual brand cigarette, or the study cigarette provided to them during this

session.

**Study Visits 2 - 3:** All procedures will be followed as outlined above in study session 1.

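### The Visit 1 procedure puts the cooling, appeal and drug-effect ratings after repeat lung-function tests and nasal sampling, while Section III.C puts them directly after the cigarette

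*Combined protocol and SAP*

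**What the plan says.** Section III.D, Study Visit 1, is a stepwise visit script. Before smoking: "Next, participants will complete computer-based spirometry testing and airwave oscillometry", followed by the first nasal epithelial lining fluid (NELF) sample. The participant then smokes the assigned cigarette ad libitum through the topography device. After that, "participants will repeat the respiratory assessment, provide the final NELF sample, and complete questionnaires (see table 1"). The second smoking session, with the forced choice, comes last. For Visits 2 and 3: "All procedures will be followed as outlined above in study session 1".

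The NELF subsection of III.D describes what sampling involves: "the nares are briefly moistened with 0.1 mL of 0.9% sterile, normal saline solution", a strip in the nostril, and a padded nose clip, with the strip left in place for 2 minutes.

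Section III.C gives a different sequence. Before smoking: "Participants will complete the pre-smoking respiratory assessments (spirometry and NELF collection"). Then: "Participants will be instructed to smoke the study cigarette. Then, questionnaires (i.e., pre/post smoking) will capture specific behavioral and subjective effects". Its sequence does not place the post-smoking respiratory tests. Table 1 carries the row heading "Respiratory Assessment (pre/post smoking") but sets no order between those tests and the questionnaires.

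The questionnaires cover cooling intensity, smell and body sensation, liking, satisfaction (mCEQ), acute drug effects (DEQ) and withdrawal (MNWS).

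**The concern.** Several of these ratings concern acute sensations, some of them felt in the nose and airway. Under Section III.D they are taken after forced breathing manoeuvres and after the nose has been wetted, packed and clipped. The respiratory tests serve Aim 3, which the plan calls exploratory. The ratings serve Aim 2, and Section III.F names sensory and appeal ratings as those where significant differences are expected, although the pilot is underpowered.

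Weaker contrasts have a particular cost here. Section I asks whether the new cigarettes give menthol smokers the same cooling perception as menthol. If ratings fade or become noisier before they are recorded, the three cigarettes look more alike, and a lost difference could be read as evidence that the cooling-agent cigarette matches menthol.

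A second mismatch sits beside the first. Section III.C labels the questionnaires pre/post smoking. The Section III.D script lists only demographic and product-use history before the cigarette and places the abuse-liability questionnaires after it.

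**Working it through.** The point is about order, so the plan has no figure to reproduce. The 60-40% power in Section III.F does not enter.

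**Step 1. The two sequences side by side.**

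| Step | Section III.C | Section III.D, Visit 1 |
|---|---|---|
| Before smoking | Spirometry, NELF; questionnaires implied by the pre/post label | Spirometry, oscillometry, first NELF; demographics and use history only |
| Cigarette | First smoking session | First smoking session |
| Next | Questionnaires | Spirometry and oscillometry repeated |
| Then | (post-smoking respiratory tests not placed) | Final NELF, then questionnaires |
| Last | Forced choice | Forced choice |

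The Section III.D steps are linked by sequence words, so staff would naturally follow them in the listed order.

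**Step 2. The delay.** The only duration given for the block between cigarette and ratings is the 2-minute NELF dwell. Spirometry and oscillometry are untimed. Read in order, the delay is therefore more than 2 minutes, with no upper limit stated. Nothing keeps it constant between visits.

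**Step 3. Which outcomes are exposed.** Section III.F lists cooling, satisfaction, forced-choice demand, topography and appeal under Aim 2. Topography is recorded while the participant smokes. The forced choice is last in both sections. That leaves the cooling, sensory, appeal, satisfaction and drug-effect ratings.

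**Step 4. What a loss would cost, as illustration only.** Take a two-sided paired t-test at alpha 0.05 with n participants and an assumed standardised paired difference dz. If a fraction L of the effect is lost, the noncentrality is dz × (1 − L) × √n. Power is the probability that the noncentral t on n − 1 degrees of freedom exceeds its critical value. For example, with n = 25, dz = 0.5 and L = 25%, the noncentrality is 0.5 × 0.75 × 5 = 1.875 and power is 43.6%. The n = 20 column applies the plan's own 20% potential dropout: 25 × 0.8 = 20.

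| Assumed dz | Assumed loss L | Power, n = 25 | Power, n = 20 |
|---|---|---|---|
| 0.8 | 0% | 97.0% | 92.4% |
| 0.8 | 10% | 93.2% | 86.3% |
| 0.8 | 25% | 82.1% | 72.1% |
| 0.8 | 50% | 48.4% | 39.7% |
| 0.5 | 0% | 67.0% | 56.4% |
| 0.5 | 10% | 57.9% | 48.0% |
| 0.5 | 25% | 43.6% | 35.7% |
| 0.5 | 50% | 22.4% | 18.5% |

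Both dz and L are assumptions. The table ignores the multiplicity adjustment that Section III.F promises for pairwise comparisons, which would lower every entry. It shows what is at stake if a loss occurs, not that one does.

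**The case against.** The strongest reply is that this is a matter of drafting. Section III.C mainly describes instruments and never places the post-smoking respiratory tests. The Section III.D sentence is a comma list under a single sequence word. Section III.E promises standard operating procedures, which could fix the order. This has some force: the sections differ in order but do not flatly contradict each other. Even if the list is read as unordered, though, the time from cigarette to rating is uncontrolled, and the plan should settle it.

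A second reply is that every participant goes through the same steps after all three cigarettes, within person and blinded. This stands against any claim of bias. Favouring one cigarette would need a delay, or a sensitivity to delay, that differs by product, and the documents show neither. It does not answer attenuation or noise.

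Third, some scales ask for a judgement of the product just smoked (liking, willingness to use again, satisfaction) rather than a present sensation, so they may fade little. That is fair. The case is strongest for cooling intensity, smell and the DEQ.

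Fourth, a NELF sample also precedes the cigarette, so the nose has already been wetted and clipped when the smoke is perceived. Reordering the post-smoking steps does not change that.

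Finally, Aim 3 concerns acute changes, so putting ratings first delays those measures. The delay is real but short and equal across conditions. It falls on an exploratory aim, and Section III.C already has the questionnaires directly after smoking.

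**Conclusion.** The concern holds as a problem of order and timing that should be corrected. Followed as written, Section III.D puts an untimed delay and a nasal procedure between the cigarette and the acute ratings at all three visits, and it disagrees with Section III.C. The likely consequence is some added noise and weaker contrasts between cigarettes. The documents give neither the length of the delay nor the rate at which the ratings fade, so the size is unknown.

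A reader might infer more, and the documents do not support it:

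- **A percentage of signal lost.** Assumed delays of 15-30 minutes and half-lives of 10-30 minutes would leave between 0.5^(30/10) = 12.5% and 0.5^(15/30) = 70.7% of a difference. Both inputs are guesses, and no scale here is shown to decay in that way.
- **Contaminated ratings.** That saline, strips and a clip disturb smell and cooling ratings is a reasonable inference, but the plan neither states nor measures it.
- **Aim 2 as a whole compromised.** No primary outcome is named, and topography and the forced choice are untouched.
- **Withdrawal change impossible to compute.** Section III.C implies a pre-smoking questionnaire. Section III.D omits it from the script, which is an inconsistency to reconcile. Withdrawal change is also not a named analysis in Section III.F.

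**What to change.** Write one order into Sections III.C and III.D:

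1. Before the cigarette: the respiratory tests and first NELF sample as now, plus an explicit pre-smoking questionnaire that includes the MNWS.
2. Immediately after the cigarette: the sensory and appeal scales, DEQ, mCEQ and post-smoking MNWS, within a stated time from the last puff.
3. Then repeat spirometry, oscillometry and the final NELF sample.
4. The forced choice last, as both sections already have it.

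The order should be the same at all three visits. Recording the clock time of the last puff and of the first rating would let adherence be checked.

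The change needs no extra participants or equipment. It delays the exploratory respiratory measures by the time taken to complete the ratings, equally in all three conditions, and makes the pre-smoking questionnaire an explicit step.

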**Protection Against Risk:**

The research protocol calls for current tobacco users. Those who participate in this study will be asked questions about nicotine and tobacco product use. Questionnaires, respiratory assessments, and user topography procedures are all non-invasive and involve minimal risk to study participants. Potential risks are as follows: a) loss of confidentiality or privacy, and b) potential for undermining smoking cessation.

**Recruitment and Informed Consent:** At first contact, all participants will be screened according to the studies inclusion/exclusion criteria. Those who are eligible will be given a brief verbal overview of the study and invited to participate. Informed consent (including a description of the nature, purpose, risks, and benefits of the study) will take place through oral explanation of the study. The voluntary nature of the study and the participant's right to withdraw at any time will be stressed during the consent process; a copy of the informed consent will be provided to the participant in written form at the time of consent for them to keep. Informed consent will be collected by IRB-approved study personnel. Recruitment script and materials (e.g., advertisements), consent forms and all study procedures will be approved by the Institutional Review Board. All participants will provide consent before any study data is collected.

There are minimal risks associated with this protocol. The protocol requires young adult (aged 21 – 29 years) current tobacco users to undergo 12 hours of nicotine abstinence on three occasions and to smoke three different types of commercially available cigarettes. The risk of side effects and adverse events are very low. These products are available at a variety of stores nationwide, without a prescription. Nevertheless, all participants will be screened for general medical precautions (e.g., pregnancy, cardiovascular disease) and monitored for adverse events during the study period. Study personnel will assess for adverse events via self-report at all visits. Any serious adverse events will be reported following guidelines outlined in the Data Safety and Monitoring Plan. We will withdraw participants who have a serious adverse event or become pregnant or begin to breastfeed. Identifying information will never be reported in any publication. Nicotine abstinence can lead to withdrawal symptoms that include irritability, anxiety, restlessness, hunger, and difficulty sleeping. The effects can be uncomfortable but are not dangerous. The risk of undermining cessation is also potential risk; however, we will only recruit users not currently engaged in a cessation attempt, and we will provide all participants at the end of the study with a referral for cessation services (e.g., Quit Line).

Protection against loss of confidentiality and privacy will be maintained by numerically coding all data, disguising identifying information, and keeping data locked in file drawers or in a secure, password-protected database. Only study research assistants and the PI will have the information that connects participant's name and ID number. All electronic data will be numerically coded and stored in a password protected database, on a password protected computer in a secure research space. Participant information will be accessible only to research staff, who are pledged to confidentiality and complete training in the ethical conduct of research (i.e., both HIPAA and CITI trainings). Identifying information will not be reported in any publication.

Whereas no assurance can be made to an individual participant that s/he will personally benefit from this research, the experience should be beneficial. The immediate benefits of this research are

scientific in nature, which in the long-term should benefit society as a whole. The study will also benefit young adult tobacco users as a group by providing information as to the abuse liability of cigarette products using synthetic cooling agents; and serve as evidence to inform regulatory action that improves public health. Overall, it is expected that the potential benefits to participants in the proposed study outweigh the potential risks.

This study is an innovative investigation that will have important public health implications. Currently, no human studies have objectively examined the behavioral (abuse liability, appeal, and user topography) implications of synthetic cooling agents added to cigarettes. Understanding this impact, will help immediately inform the science base needed for the FDA to implement appropriate product-specific regulations.

